	
treatment-emergent (TEAEs) will be summarized. A TEAE is an AE that starts or increases in severity any time after the first administration of any study drug up to 30 days following the last administration of any study drug. AE severity is rated by the Investigator according to CTCAE version 5.
 
A high-level safety summary will display the numbers of patients within each treatment arm and overall who experience one or more AEs in each of the following categories:
 
• All TEAEs regardless of severity or presumed relationship to study drug• TEAEs judged related to study drug• All TLS SMQ TEAEs• TLS SMQ TEAEs judged related to study drug• Treatment-emergent SAEs• TEAEs leading to a delay in the administration of study drug• TEAEs leading to a reduction in the protocol-specified dose of study drug• TEAEs leading to discontinuation of study drug• TEAEs leading to withdrawal from study treatment• TEAEs leading to death. 
The base summary of TEAEs will show within- and between-treatment-arm incidence rates for each MedDRA primary System Organ Class (SOC) and/or Preferred Term (PT) by highest reported CTCAE severity grade and overall. A separate summary will be produced each of the AE subsets listed above. Additional AE summaries may be produced using safety data from subsets of patients and/or characterized using additional SMQs.
 
PD Analyses
 
Summary of baseline biomarker values will include within- and between-treatment-arm descriptive statistics. If there are sufficient numbers of patients achieving remissions for an analysis to be informative, a logistic regression model will be fit to examine the relationship between potential biomarkers and the independent binary variables complete remissions, combined complete remissions, and combined remissions during the study.

--	---

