Study Design	
This is an open-label, randomized, two-stage clinical study. During Stage 1, 26 patients will be randomized into each of the 2 treatment arms (52 patients total) stratified by prior response to venetoclax in combination with azacytidine or decitabine:
 
• Refractory (ie, failed to achieve a CR/CRI or achieved a CR/CRI with duration <90 days)• Relapsed (ie, reoccurrence of disease following a CR/CRI with duration ≥ 90 days). 
Lead-in Cohort
 
As an additional safety measure given the unique patient population and outpatient treatment administration, a separate lead-in cohort of approximately six patients (at least three patients in each treatment arm) will be enrolled, treated, and evaluated for dose-limiting toxicities (DLTs). If a DLT is observed, dose de-escalation will occur as outlined in Appendix F. Should no additional DLTs be observed during Cycle 1, Amendment 2 be approved, and the Data Safety Monitoring Board (DSMB) confirm safety, randomization into Stage 1 will commence as outlined in the protocol. However, should an additional DLT be observed at Dose Level 1, a clinical meeting would be scheduled to discuss the utility/futility of continuing the study as currently designed.
 
If patients treated in the lead-in cohort are still on study when Amendment 2 is approved and the DSMB has confirmed safety, they may be permitted to shift to the higher alvocidib (ALV) dose regimen, ie, ALV 50 mg/m² IV bolus, per investigator discretion.
 
Stage 1
 
A futility analysis will be conducted at the end of Stage 1 to determine if the combined CR rate meets the threshold for continuing the study. Using an alpha spending function to control the overall level of significance, the threshold is that the one-sided p-value be <0.60525 in order to initiate Stage 2; which is achieved if there are more than 4 combined CRs among the 52 Stage 1 patients. No additional patients will be enrolled if the number of patients with combined CR at the end of Stage 1 fails to meet this criterion.
 
Stage 2
 
Determination of the recommended alvocidib-based treatment arm for Stage 2 will be subjective, comparing the response rates, relative safety, and the risk-benefit ratio of the two Stage 1 treatment arms. An additional 76 patients will be enrolled into the treatment arm selected for Stage 2 for a total of 102 patients (26 and 76 from Stages 1 and 2, respectively). The combined CR rate (primary

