11.2 Sample Size

This study follows a 2-stage adaptive design that allows for continuing patient recruitment into the **recommended** alvocidib-based treatment arm used in Stage 1. It is designed to test the null hypothesis that the combined CR rate is 10% against the alternative that the combined CR rate is >10%. Up to 128 eligible patients **from Stage 1 and Stage 2** will be evaluated **for efficacy**. **Patients enrolled in the safety lead-in cohort will not be included in the efficacy analyses since they will receive a lower dose of alvocidib than the patients enrolled in Stage 1 and Stage 2.** Assuming the actual combined CR rate is 20%, the study has 80% power at the one-sided 2.5% level of significance. The underlying statistical properties of this design are based on a 2-stage sequential design where the overall one-sided 2.5% level of significance is protected using error spending. Forty percent of total information will be accumulated prior to the interim analysis at the end of Stage 1, where 10% of the overall alpha will be used. All data from Stages 1 and 2 will be used for the statistical test of combined CR rate at the end of the study, hence the adaptive component of this design (dropping 1 of the 2 treatment arms at the end of Stage 1) does not affect the overall type-1 and type-2 error probabilities (see [Appendix G](#)).

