APPENDIX G – ADDITIONAL STATISTICAL INFORMATION

The following SAS programming statements and SAS output were used to confirm the statistical properties of the study design.

```
proc seqdesign boundaryscale=pvalue;
  design
    alpha=0.025
    alt=upper
    beta=0.2
    info=cum(2 5)
    method=errspend(1 10)
    nstages=2
    stop=both;
  samplesize model=onesamplefreq(nullprop=0.1 prop=0.2);
run;
```

DESIGN INFORMATION	
Statistic Distribution	Normal
Boundary Scale	p-Value
Alternative Hypothesis	Upper
Early Stop	Accept/Reject Null
Method	Error Spending
Boundary Key	Both
Alternative Reference	0.1
Number of Stages	2
Alpha	0.025
Beta	0.2
Power	0.8
Max Information (Percent of Fixed Sample)	101.6893
Max Information	798.1471
Null Ref ASN (Percent of Fixed Sample)	77.45185
Alt Ref ASN (Percent of Fixed Sample)	91.0849

METHOD INFORMATION

Boundary	Method	Alpha	Beta	Alternative Reference	Drift
Upper Alpha	Error Spending	0.02500	.	0.1	2.82515
Upper Beta	Error Spending	.	0.20000	0.1	2.82515

BOUNDARY INFORMATION (p-Value Scale); Null Reference = 0

Stage_	Information Level			Alternative	Boundary Values	
				Reference	Upper	
	Proportion	Actual	N	Upper	Beta	Alpha
1	0.4000	319.2588	51.08141	1.78678	0.60525	0.00250
2	1.0000	798.1471	127.7035	2.82515	0.02407	0.02407

SAMPLE SIZE SUMMARY

Test	One-Sample Proportion
Null Proportion	0.1
Proportion	0.2
Test Statistic	Z for Proportion
Reference Proportion	Alt Ref
Max Sample Size	127.7035
Expected Sample Size (Null Ref)	97.26562
Expected Sample Size (Alt Ref)	114.3863

SAMPLE SIZES (N) One-Sample Z Test for Proportion

Stage_	Fractional N		Ceiling N	
	N	Information	N	Information
1	51.08	319.3	52	325.0
2	127.70	798.1	128	800.0

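### The pooled Stage 1 futility rule assumes one response rate in both arms, so its 2% false-stop allowance and the claim that dropping an arm leaves type 2 error unchanged do not hold for a 20% arm paired with a weaker one

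*Protocol*

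**What the plan says.** Under Study Design, the Protocol synopsis says that "26 patients will be randomized into each of the 2 treatment arms (52 patients total") and sets the Stage 1 condition on the p-value scale: "the threshold is that the one-sided p-value be <0.60525 in order to initiate Stage 2". It translates this into a count, "which is achieved if there are more than 4 combined CRs among the 52 Stage 1 patients". The rule is binding: "No additional patients will be enrolled if the number of patients with combined CR at the end of Stage 1 fails to meet this criterion". SAP Section 2 repeats it under its planned text. No per-arm condition appears anywhere.

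Stage 2 continues a single regimen: "An additional 76 patients will be enrolled into the treatment arm selected for Stage 2 for a total of 102 patients". The arm is chosen subjectively on response rates, relative safety and risk-benefit (Protocol 4.1 and 4.2).

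Appendix G derives the boundary from a one-sample proportion model (0.1 against 0.2) with beta 0.2 and "method=errspend(1 10"), which spends one tenth of each error at Stage 1. Protocol 11.2 and SAP Section 4 then state that dropping one arm changes neither error probability. Neither document gives operating characteristics for arms with different rates.

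**The concern.** The gate asks whether 52 patients on two regimens, taken together, respond often enough. The decision it controls is whether to put 76 more patients on one of those regimens. The two questions coincide only when the arms share a rate. If they differ, the weaker arm supplies half the patients and few of the responses, and a regimen at the 20% target rate can be stopped because of the other arm.

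The protocol itself gives reason to expect a difference. Section 2.7 says that monotherapy has not been evaluated for efficacy, and Section 2.4 suggests alvocidib may work particularly well when cytarabine follows. At stake is the type 2 error for a single active regimen, which the plan says is unaffected by the adaptive step.

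**Working it through.** **1. Reproduce Appendix G.** Inputs: one-sided alpha 0.025, beta 0.2, information fraction 2/5 = 0.40, and one tenth of each error spent at Stage 1 (alpha 0.0025, beta 0.02). Solving the two-stage design with binding futility gives drift 2.82515.

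- Stage 1 drift: 2.82515 × √0.4 = 1.78678.
- Futility bound: z = 1.78678 + Φ⁻¹(0.02) = 1.78678 − 2.05375 = −0.26697, so p = 0.60525.
- Maximum N: 2.82515² × 0.2 × 0.8 / 0.1² = 127.70, and 0.4 × 127.70 = 51.08.
- Final boundary: p = 0.02407.

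All agree with the printed output.

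**2. Check the count.** With X ~ Bin(52, 0.1), P(X ≥ 5) = 0.6046, which is below 0.60525, and P(X ≥ 4) = 0.7768, which is not. The count rule therefore matches the boundary for 52 pooled patients.

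**3. Stop probability for a 20% arm.** Let A ~ Bin(26, 0.20) and B ~ Bin(26, p), independent. The rule stops the trial if A + B ≤ 4:

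P(stop) = Σ (k = 0 to 4) P(A = k) × P(B ≤ 4 − k).

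The rate p is an assumption, shown here over a range. At p = 0 the sum is P(A ≤ 4) = 0.0030 + 0.0196 + 0.0614 + 0.1228 + 0.1765 = 0.3833. At p = 0.20 it is P(Bin(52, 0.2) ≤ 4) = 0.0137.

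**4. Power of the 102-patient test.** Assume the 20% arm is always selected and there is no early stop for efficacy. The exact critical value at 0.02407 is 18. Power is Σ P(A = k) × P(gate passes given k) × P(Bin(76, 0.2) ≥ 18 − k). With no gate it is P(Bin(102, 0.2) ≥ 18) = 76.0%.

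| Other arm | Stop at Stage 1 | Power | Loss against no gate (points) |
|---|---|---|---|
| 20% | 1.4% | 75.4% | 0.6 |
| 15% | 3.7% | 74.2% | 1.8 |
| 10% | 9.1% | 71.5% | 4.5 |
| 5% | 19.8% | 65.3% | 10.7 |
| 0% | 38.3% | 53.5% | 22.5 |

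If the final test is a z-test with the null variance, the critical value is 17. Power is then 82.5%, 77.7%, 70.5% and 56.7% with the other arm at 20%, 10%, 5% and 0%, against 83.3% with no gate. The pattern is the same.

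**5. Effect of a per-arm route.** Stop only if A + B ≤ 4 and the larger arm count is below m. Type I error is exact for the 102-patient test with both arms at 10%, the arm with more responses selected and ties split evenly.

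| Quantity | Pooled rule only | Plus ≥4 of 26 | Plus ≥3 of 26 |
|---|---|---|---|
| Stop, 20%/10% | 9.1% | 7.9% | 4.3% |
| Stop, 20%/5% | 19.8% | 15.1% | 7.2% |
| Stop, 20%/0% | 38.3% | 20.7% | 8.4% |
| Stage 2 opens, 10%/10% | 60.5% | 62.4% | 73.9% |
| Type I error, 10%/10% | 1.82% | 1.86% | 1.95% |

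**The case against.** Pooling can be defended as a design choice. Both arms contain alvocidib, Protocol 11.2 describes one combined CR rate, and it says that all Stage 1 and Stage 2 data enter the final test. If that means 128 pooled patients, a pooled gate matches the analysis, and unequal arms are not the alternative the study was sized for. This stands as far as it goes. But the same documents put 102 patients on the selected regimen, and the statement about dropping an arm carries no equal-rate condition.

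A reader might infer three stronger things, which the documents do not support.

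- **That an active regimen is falsely stopped in 20% to 38% of trials.** This needs the other arm at 5% down to 0%, and neither document gives such a rate. The only inactive rate the plan defines is 10%, where the figure is 9.1%. Lower rates cannot be excluded, but they are sensitivity cases.
- **That an arm with 3 or 4 of 26 already passes the plan's own p<0.60525.** That boundary belongs to the pooled look at 40% of the information. The plan has no per-arm p-value criterion.
- **That the gate alone costs the study its 80% power.** With an exact test, the 102-patient analysis has 76.0% power with no gate at all. The gate's own share is the loss column in the working.

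It is also true that SAP 7.1 plans no formal efficacy interim analysis, that the study closed with 4 Stage 1 patients, and that the gate was never applied.

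**Conclusion.** The point holds as a limit on what the plan can claim. The 0.02 of beta spent at Stage 1, and the statement that dropping an arm leaves type 2 error unchanged, are correct only when both arms have the 20% rate. With the other arm at the design's own null of 10%, a 20% arm is stopped in 9.1% of trials, more than four times the 2% spent, and power falls by 4.5 points. The effect grows to a 38.3% stop rate and a 22.5-point loss if the other arm has no responses.

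The stop probabilities are exact, given 26 independent patients per arm and the assumed rate in the other arm. The power figures also assume that the 20% arm is always selected and is tested exactly on 102 patients. The type I error calculated here stays below 2.5% under the present rule, so the objection is to the type 2 part of the statement. This concerns the design of record and any reuse of it.

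**What to change.** 1. **Error statement.** In Protocol 11.2, SAP Section 4 and Appendix G, limit the type 2 error claim and the 2% Stage 1 figure to equal arm rates. Report the exact stop probabilities and power for a 20% arm with the other arm at 20%, 15%, 10%, 5% and 0%.

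2. **Gate.** In the synopsis Stage 1 paragraph and the planned text of SAP Section 2, keep the pooled rule and add a per-arm route, for example: *Stage 2 may open if CR/CRi is seen in at least 5 of all 52 Stage 1 patients, or in at least 3 of the 26 patients of either arm.* Leave the choice of arm to the existing criteria, so that the count does not override safety or risk-benefit and there is no ambiguity when both arms qualify. Present 3 of 26 as a choice based on its operating characteristics, not as an application of p<0.60525.

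3. **Consistency.** Reconcile the gate with SAP 7.1, because the SAP declares that it supersedes the protocol's statistical considerations.

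The cost is wording and a short calculation, with no increase in the planned maximum. The downside is that Stage 2 opens more often when both arms are at 10% (73.9% against 60.5%) and exact type I error rises from 1.82% to 1.95%. A 4-of-26 route is cheaper (62.4% and 1.86%) but leaves stop rates of 7.9%, 15.1% and 20.7% with the other arm at 10%, 5% and 0%. The descriptive tables for the closed trial are unaffected.

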1. INTRODUCTION

1.1 Acute Myeloid Leukemia

The clinical objective of induction chemotherapy is to obtain 'first CR' (complete remission with recovery of blood counts) in as many newly diagnosed AML patients as possible. Attaining initial CR enables application of further therapies of curative intent (consolidation and transplant). Once CR is obtained, survival also varies as a function of age, cytogenetic risk status, and likely, by minimal residual disease (MRD). In patients with unfavorable-risk AML, <60% achieve CR, many patients relapse quickly, and survival among responders is woefully low with 5% to 10% experiencing chemotherapy-related deaths due to severe toxicity. These data amplify the decades' long tragedy and debilitating nature of available treatments for newly diagnosed AML patients, particularly for older patients >60 years, those with adverse and complex cytogenetics, and patients with secondary AML.

Until recently, the best treatment for unfit patients with AML was ill defined; however, results from clinical trials of venetoclax in combination with hypomethylating agents (HMAs) demonstrated an impressive complete response rate of 54% (CR/CRI) with a median time to first response of 1.4 months and median duration of response 8.1 months providing a new option for patients previously considered 'unfit' for intensive induction regimens [1]. For patients who relapse after venetoclax/HMA therapy, second-line therapy is not defined. There remains an unmet medical need to identify safe and effective outpatient treatment options for this patient population while preserving their quality of life.

1.1.1 Role of MCL-1 in AML

The ability to resist cell death is an important hallmark of all cancer cells, allowing them to divide uncontrollably [2,3]. The BCL-2 family of polypeptides has been widely studied as regulators of cell death [4]. Because members of this protein family can exhibit pro- or anti-apoptotic functions, they are highly involved in the development of cancer and in mechanisms of resistance to many therapeutic agents. The myeloid leukemia cell-1 (MCL-1) gene is the predominant BCL2 family member expressed in primary AML samples. Tumor resistance to targeted therapies limits effectiveness of current clinical regimens. Overexpression of MCL-1 has been shown to convey resistance to apoptosis induced by a number of different treatments, including etoposide, *in vitro* [5,6]. Other studies have indicated that MCL-1 expression can be induced rapidly in response to a number of DNA-damaging agents [7,8].

Alvocidib (flavopiridol), a potent cyclin-dependent kinase (CDK) inhibitor, downregulates the expression of MCL-1 through inhibition of CDK 9, which, in turn, inhibits tumor growth. Studies have shown that alvocidib suppresses MCL-1 expression [9,10] and acts synergistically with other chemotherapeutic agents like daunorubicin and cytarabine. Through use of mitochondrial (BH3) profiling, the mechanism by which apoptosis is suppressed in a population of

cells can be determined. Mitochondrial sensitivity to NOXA BH3 peptides suggests dependence on MCL-1 to mediate resistance to apoptosis. Early studies have shown that MCL-1 dependence can predict the clinical activity of alvocidib in AML patient samples and suggests an important role for MCL-1 activity in predicting alvocidib activity [11]. TMS1 is a NOXA mimetic that is used to measure MCL-1 dependency in addition to other potential molecular (genetic) targets [12].

1.1.2 Relapsed and/or Refractory AML

A significant number of patients receiving initial induction chemotherapy for AML either do not achieve remission or relapse after induction of remission. According to the venetoclax package insert, 58% of patients treated with venetoclax plus low-dose cytarabine (LDAC), 39% of patients treated with venetoclax plus azacytidine, and 38.3% of patients treated with venetoclax plus decitabine did not achieve CR or CRh. Although venetoclax, a BCL-2 inhibitor, is transforming the treatment landscape for AML and other hematologic malignancies, existing standard-of-care AML therapies do not adequately attain sufficiently high rates of CR, duration of CR, or satisfactory survival rates in the majority of AML patients who are unfit or considered elderly.

1.2 Rationale

Acute myeloid leukemia (AML) continues to be one of the highest unmet medical needs, due to very short survival from time of diagnosis (median <1 to 2 years). Shorter survival of AML patients is directly correlated with the presence of unfavorable cytogenetics and multiple adverse clinical features including advanced age and reduced performance status. Initial complete remission still remains elusive in approximately 40-60% of AML patients resulting in progression and shortened survival. The targeting of anti-apoptotic proteins, such as BCL-2 and MCL-1, in AML is thought to be a prime therapeutic strategy moving forward with novel and/or potent compounds [13].

Clinical trials with alvocidib (both as monotherapy and in combination with cytarabine/mitoxantrone) have shown promising activity to date. These trials have spanned the front-line setting for newly diagnosed high-risk population to the relapsed refractory setting. Recently presented at the American Society of Hematology (ASH) 2018 Annual Meeting were the Stage 1 results of the Zella 201 trial demonstrating a 77% response (CR/CRI) in evaluable refractory AML patients receiving alvocidib/cytarabine/mitoxantrone combination therapy. The median MCL-1 dependence score (flow cytometry-based assay) was 53% in that patient population [14].

Interestingly, there appears to be an opportunity to overcome MCL-1 dependent venetoclax resistance by inhibiting MCL-1 signaling with alvocidib. In vitro work has shown that AML cell lines can be re-sensitized to venetoclax, or other BCL-2 inhibitors, by downregulating MCL-1 via alvocidib [15,16]. Mechanistically, leukemic stem cells are dependent on MCL-1 which may allow alvocidib to help deepen a response [17]. Clinically, it is thought that patients who have been treated with venetoclax will switch the dependency of apoptosis in leukemic blasts from BCL-2 to MCL-1.

2. DRUG INFORMATION – ALVOCIDIB

A comprehensive review of alvocidib is contained in the [Investigator's Brochure](#) provided by the Sponsor. This document should be reviewed prior to initiating the study.

2.1 Background

Alvocidib (formerly flavopiridol) was discovered and synthesized from an alkaloid isolated from the stems and leaves of *Dysoxylum binectariferum* (India). [name] and colleagues at the National Cancer Institute (NCI) first determined alvocidib cell cycle arrest/growth inhibition properties in 1992.

2.2 Chemistry

2.3 Drug Description

Alvocidib hydrochloride is supplied as a sterile, intravenous, nonpyrogenic, yellow-colored aqueous solution. Each vial contains 50 mg of alvocidib base (10 mg/mL). Alvocidib is to be diluted with either 0.9% Sodium Chloride Injection, USP, or 5% Dextrose Injection, USP, prior to infusion, providing solutions between 0.09 to 1.0 mg/mL alvocidib.

2.4 Mechanism of Action

Alvocidib is a potent cyclin-dependent kinase (CDK) inhibitor with selectivity for CDKs 9, 1, 2, 4 and 7 [18,19,20]. The greatest inhibition (K_i of 3 nM) was observed with CDK 9 [21]. Alvocidib-induced apoptosis results at least in part from inhibition of multiple serine-threonine CDKs leading to changes in gene expression of critical survival and proliferative genes including BCL-2, myeloid cell leukemia-1 (MCL-1) and c-myc [22,23,24]. Whereas inhibition of CDK 2 and CDK 4 contributes to cell cycle arrest in G1 and G2, alvocidib-triggered inactivation of the CDK 9/cyclin T complex (also known as PTEF-b) inhibits the activating phosphorylation of RNA polymerase 2 and diminishes mRNA synthesis [25,26]. Consequently, alvocidib-treated cells are unable to synthesize transcripts encoding polypeptides, such as cyclin D1 and c-myc, which are expressed in a cell cycle-dependent manner [27].

Inhibition of CDK 9, which is involved in the regulation of transcription by RNA polymerase 2, is postulated to be a key event in the inhibition of transcription observed following alvocidib treatment. Effects on CDK 9 may be particularly relevant to inducing apoptosis in malignant hematopoietic cells [28].

These observations, coupled with the ability of alvocidib to kill non-cycling cells, suggested that alvocidib might be particularly effective when administered first and then followed several days later by cytarabine. Therapeutically achievable alvocidib concentrations induced apoptotic cell death in bone marrow leukemic blasts in vitro and that alvocidib-treated blast cultures exhibited increased sensitivity to the subsequent pro-apoptotic effects of cytarabine relative to either agent alone [29].

